In human studies, single-dose intranasal OXT administration is associated with enhanced emotion recognition/mentalizing²⁶, face identity²⁷, and increased attention to the eye region²⁸. In ASD, studies find reduced plasma OXT levels²⁹, absence of normal developmental increase in oxytocin blood levels with age^{30,31} and variations in the OXT receptor (OXTR)^{32,33}. The greatest excitement has surrounded replicated findings of improved attention to the eye region, mentalizing abilities, and partner preference from single-dose OXT challenge studies in ASD³⁴⁻³⁶. The effects of intranasal oxytocin (INOXT) and its ability to cross the BBB have yet to be determined. INOXT has been shown to affect functional responses in several brain regions including the medial prefrontal cortex, anterior insula, orbitofrontal cortex, amygdala, and ventral striatum.

The convergence of evidence on the impact of OXT/AVP on social behaviors has fueled several investigations of the therapeutic potential of these compounds in neuropsychiatric conditions characterized by social impairment. The vast majority of human studies have been conducted on OXT compounds. Pilot data from oxytocin monotherapy trials indicate daily, intranasal OXT is safe and feasible in adult^{37,38} and pediatric populations^{37,39} delivered over a period of 6 weeks^{37,40} to seven months³⁸. The applicant and colleagues recently published on a dose-finding, safety trial of intranasal OXT in 15 adolescents with ASD⁴⁰. Four doses were tested every two weeks for 12 weeks. Follow-up testing was conducted at 16 and 24 weeks. Mild to moderate side effects were reported including irritability, headache, upper respiratory infections, and decreased appetite. In this small open-label trial, significant pre-post changes were found on measures of social cognition, social behavior, anxiety and repetitive behaviors with carry-over effects found at 3-month follow-up on social cognition, repetitive behavior, and functional communication skills. Overall, preliminary findings from multi-dose OXT studies support medium to small effects but require replication in well-powered, controlled trials⁴¹.

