study⁴⁰ indicate that the medication was very well tolerated compared to placebo (see pilot studies section). Side effects of IN-OXT may include nasal irritation, runny nose, or tearing of the eyes, as well as an allergic reaction. Additional rare side effects reported in single cases and of unknown relationship with the medication include unusual bleeding, convulsions, nausea, drowsiness, headache, anxiety, and sad mood. Uterine contractions may occur in women and are more likely to occur in pregnant women, especially at the end of pregnancy. Estrogen mediates Pitocin®'s effect on uterine muscle. Large doses of intravenous OXT decrease both systolic and diastolic blood pressure through a transient relaxation of vascular smooth muscle. Any OXT-induced decrease in blood pressure is followed by a mild but sustained increase. IN-OXT, which will be used in the present study, has not been found to substantially affect blood pressure. The recent pilot data in pediatric ASD did not find effects on blood pressure. However, the proposed trial will continue to monitor blood pressure given the great need for safety data on this high-profile compound.

Rationale for Intranasal Administration

OXT is metabolized by chymotrypsin in the GI tract and therefore is not administered orally. Currently, the only form of OXT that is available in Canada and the US is the intravenous form and although this formulation has been found to produce behavioral effects, it is invasive to administer and the extent to which this formulation crosses the blood-brain barrier (BBB) is not known. However, several recent studies support the impact, direct or indirect, of peripherally administered OXT on centrally mediated processes. Ring et al.⁴⁸ investigated anxiolytic effects of centrally and peripherally administered OXT in male mice. Peripheral administration was found to produce behavioral effects but required substantially larger doses to produce similar effects as centrally administered OXT. These researchers argue, that "the anxiolytic-like effects of peripherally administered OXT can be accounted for by the passage of relatively small, but sufficient, amounts of the peptide across the BBB into the CNS" 50.

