Results: NETT participants improved on the social behavior composite capturing nonverbal communication, social relations, and empathic responding skills at endpoint compared to controls ($B=-.31$, $SE=.14$, $p=.04$). No group differences were found on the social cognition composite ($B= 0.00$, $SE=.13$, $p=.98$). Outcomes at a three-month follow-up interval were not significant suggesting a potential waning effect of the CBI intervention over time ($B=-.14$, $SE=.19$, $p=.47$). Moderator analyses indicated higher verbal IQs were associated with social behavior improvements in NETT but not controls ($B=-.02$, $SE=.01$, $p=.03$). Results also show improvements on low-intensity (i.e. more ambiguous) facial emotion identification items in NETT but not controls (estimate =1.1, $p<.01$, Cohen's $d = .56$). Poor quality data and compliance issues limited the imaging sample to approximately

Confidential

Rush University Medical Center

half of the behavioral data. In this subset of participants, NETT increases activation in mentalizing regions including the medial prefrontal cortex and temporal pole junction during an averted eye gaze task (Figure 2)⁵⁰.

Summary: Our findings demonstrate short-term, specific treatment effects of targeted CBI-based SST curricula of NETT on core social-communication behaviors in youth with ASD. The limited effects on social cognitive processes are supported by two recent Cochrane reviews^{14,51}.

Intranasal oxytocin for the treatment of children and adolescents with autism spectrum disorder

ClinicalTrials.gov lists 22 clinical studies of intranasal oxytocin (IN-OXT) in ASD which are actively or recently completed recruitment. Of the handful of published findings in this area, the vast majority include small single-dose challenge studies in adults with ASD. Studies suggest a medium effect size on measures of social cognition and social impairment⁴¹. Overall, IN-OXT was well-tolerated and had a side effect profile including restlessness, increased energy, and increased irritability. The PI and collaborators published on a modified maximum dose-finding and safety study of a 12-week oxytocin daily monotherapy in verbal, youth with ASD⁵². The highest dose evaluated was .4 IU/kg/dose and was well-tolerated. Several measures of social behavior, repetitive behavior, and social cognition demonstrated change at endpoint (12 weeks) as well as at a 3-month follow-up post-discontinuation of IN-OXT⁴⁰.

2. Study Aims

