3. Patients with a medical history of neurological disease, including, but not limited to, epilepsy/seizure disorder (except simple febrile seizures), movement disorder, tuberous sclerosis, fragile X, and any other known genetic syndromes, or known abnormal brain MRI/structural lesion.
4. Pregnant female patients, sexually active female patients on hormonal birth control and sexually active females who do not use at least two types of non-hormonal birth control.
5. Patients with evidence or history of malignancy or any significant hematological, endocrine, cardiovascular (including any rhythm disorder), respiratory, renal, hepatic, or gastrointestinal disease.
6. Patients with one or more of the following: hemophilia (bleeding problems, recent nose and brain injuries), abnormal blood pressure (hypotension or hypertension), drug abuse, immunity disorder or severe depression.
7. Patients who are currently taking OXT or have taken IN-OXT in the past with no response.
8. Patients who have an Aberrant Behavior Checklist (ABC) Irritability subscale score > 19 at screening/baseline
9. Patients with sensitivity to OXT or any components of its formulation.
10. Patients unable to tolerate venipuncture procedures for blood sampling.
11. Patients in foster care for whom the state is defined as a legal guardian.
12. If they have an arrhythmia present on ECG, that upon consultation with a cardiologist, is deemed to be clinically significant.
13. Patients with any of the following clinical lab results
 - a. ALT/AST levels of \geq 5 times the upper limit of normal, or if clinical jaundice occurs
 - b. Sodium levels of > 152 mmol/L or < 128 mmol/L
 - c. Potassium levels of > 6 mmol/L in a non-hemolyzed sample
 - d. Glucose levels of > 11 mmol/L or < 2.8 mmol/L
 - e. Hemoglobin levels of < 100 g/L
 - f. BUN levels of > 100 mmol/L
 - g. Creatinine levels of > 100 μ mol/L
 - h. Osmolality levels of > 330 mmol/kg

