- b. *Social Responsiveness Scale*⁵⁵. The SRS has been developed to measure autism related symptoms and focuses more on social function than social cognition. The SRS measures social behaviors such as social awareness, information processing, and social motivation and yields a quantitative score that has been useful in endophenotyping studies of ASD. It is a well validated measure in this population, with an internal consistency 0.93 to 0.97, test-retest reliability of 0.77 to 0.85, and inter-rater reliability 0.74 to 0.91. Validity has been examined in terms of discriminant validity, concurrent validity, structural validation, and factor analytic studies.
- c.

2. Social behavior

- a. *Pervasive Developmental Disorders Behavior Inventory-Screening Version*⁶¹. The PDDBI-SV assesses both maladaptive and adaptive social behaviors presenting in children with ASD. The PDDBI-SV yields a measure of social impairment (SOCDEF raw & T scores). This is a co-primary outcome measure in a larger NIH-funded oxytocin monotherapy trial⁵⁷ and is included in this study to help provide consistency across studies in measuring critical social behavior outcomes.
- b. *Aberrant Behavior Checklist (ABC)*. The ABC focuses on problem behaviors in 5 domains: irritability, attention, repetitive behaviors, unusual speech, and social withdrawal (SW). The ABC-SW is a co-primary outcome in the NIH-funded OXT monotherapy trial and will be used in this study to provide methods for comparison across trials.
- c. *Sensor-based measures of social-communication*. This assessment will utilize a computer-based package to automatically detect target social behaviors including eye-gaze, facial

expressions, use of emotion words, quality of speech, and gestural communication. The package includes three system components: wearable eye-tracking device (e.g. Tobii glasses), 3-D cameras, and audio recordings of voice recognition software.

3. *Social cognition.* Social cognition requires distinct but related mental mechanisms including perceiving people and actions, perceiving emotional states of others, evaluating beliefs and intentions, sharing attention, and reflecting others' beliefs and states (Perlman, Vander Wyk, & Pelphrey, 2012). Exploratory outcomes of specific social cognitive domains will be tested and will inform development of a brain-based behavioral toolbox for use in future trials. All measures will be administered on a Tobii T-60 eye-tracker.

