ICH E6 defines an AE as any untoward medical occurrence in a patient or clinical investigation subject administered a pharmaceutical product regardless of its causal relationship to the study treatment. An AE can therefore be any unfavorable and unintended sign (including an abnormal laboratory finding that is not directly obtained for purposes of the study), symptom, or disease temporally associated with the use of medicinal (investigational) product. The occurrence of an AE may come to the attention of study personnel during study visits and interviews of a study subject presenting for medical care, or upon review by a study monitor. All AEs including will be captured on the appropriate source documentation, the structured AE rating form. Information to be collected includes event description and clinician's assessment of severity.

8.2. Treatment Emergent Adverse Events (TEAEs).

Safety analysis will focus on TEAEs. Medical and behavioral conditions will be evaluated at screening and baseline, and will only be considered TEAEs if the severity increases significantly after a participant has completed a treatment session. All TEAEs will be documented during the course of the study regardless of relationship to treatment. All TEAEs will be followed to adequate resolution. If a TEAE is also a serious adverse event (SAE) and/or Unexpected Problem (UP), the SAE or UP forms will also be completed. If a TEAE is both a SAE and UP, only the SAE form and the AE FORM will be completed.

8.3. *Suicidality Assessment.*

Suicidality assessments will be completed for each participant during visits with Study clinicians. The clinician will determine if the participant understands the concept of death and making one's self die or hurt. If the participant is able to understand these concepts, they will be asked if they have any thoughts about wanting to die, wanting to hurt themselves, wanting to kill themselves, and if s/he has done anything to hurt himself/herself so s/he would die or have done anything to hurt himself/herself for any other reason. If the participant is deemed not to understand these concepts, his/her caregiver will be asked the above questions. The caregiver will also be asked to rate if this is a significant changes in severity or frequency from the participant's behavior at baseline.

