Official title: Integrated Oxytocin and Nonverbal, Emotion Recognition, and Theory of Mind

Training for Children With Autism Spectrum Disorder

NCT number: NCT02918864

Document date: 2/8/2021

Statistical Analysis Plan

Data Reduction and Outcome Variables. Safety and tolerability will be evaluated by comparing group differences on total counts and domains of the AE form and ratings on parent satisfaction surveys respectively. Efficacy analysis will follow analytic procedures used to derive social behavior impairment (SBI) and social cognition (SC) composites for the Seaver-NETT RCT16. First, principal components analysis (PCA) with promax rotation will be conducted on the primary social behavior impairment measures, the Nonverbal Communication and Social Relations subscales of the Children's Communication Checklist-2 (CCC-2) and the total score of the Griffith Empathy Scale (GEM). A separate PCA will be conducted on the primary social cognition outcomes, the Reading the Mind in the Eyes Test (RMET) and Diagnostic Analysis of Nonverbal Accuracy-2 (DANVA-2). The PCAs are used to confirm that these measures contribute to previously identified constructs in a field with no viable outcomes for higher-order core social impairments as well as to minimize floor and ceiling artifacts, effects of variability in response, and other sources of measurement error.

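### ABC-Irritability and weight are collected in both arms, but the safety analysis uses neither, so a moderate between-arm shift that is not recorded as an adverse event could go unreported

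*Protocol*

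**What the plan says.** **Effects named.** Protocol section 1 summarises the team's own open-label study in 15 adolescents: "Mild to moderate side effects were reported including irritability, headache, upper respiratory infections, and decreased appetite". Section 1.1 says of the published intranasal oxytocin studies that the drug "had a side effect profile including restlessness, increased energy, and increased irritability".

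**Measures collected.** Section 4.2 describes the ABC: "The ABC focuses on problem behaviors in 5 domains: irritability, attention, repetitive behaviors, unusual speech, and social withdrawal (SW"). Appendix A schedules it at screening and Weeks 6, 12, 16 and 24. Section 4.3 schedules weight at screening, baseline, Week 12 and Week 24. Neither is limited to one arm; section 4.1 makes only the Week 12 ECG and safety labs optional for the play group.

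**Uses given.** The irritability subscale has one stated use, as an exclusion in section 3.3: "Patients who have an Aberrant Behavior Checklist (ABC) Irritability subscale score > 19 at screening/baseline". The ABC outcome singled out in section 4.2 is social withdrawal: "The ABC-SW is a co-primary outcome in the NIH-funded OXT monotherapy trial and will be used in this study".

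**Safety analysis.** Protocol 8.8 compares the arms on AE-form total scores and domains, and on satisfaction surveys. The SAP, under Data Reduction and Outcome Variables, plans "comparing group differences on total counts and domains of the AE form" plus parent satisfaction ratings. Protocol 8.2 centres safety on treatment-emergent events and says that conditions evaluated at screening and baseline "will only be considered TEAEs if the severity increases significantly after a participant has completed a treatment session".

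**The concern.** Safety and tolerability are part (A) of the primary aim (Protocol 2.1), and Protocol 8.9 offers safety information as a main return from a trial it calls potentially underpowered. Two effects that the protocol itself names each have a graded measure, taken repeatedly in both arms, with no planned analysis.

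The remaining route is the AE form, and two features limit it for this purpose. First, entry allows ABC-Irritability scores up to 19, so children may start with some irritability. For them a worsening becomes a treatment-emergent event only after a clinician judges it significant, and no threshold is stated. Second, Protocol 8.8 speaks of total scores while the SAP speaks of total counts, and counts lose gradation. The AE raters are also unblinded (Protocol 3.1), and the form's items and domains are not listed, so a separately reported irritability domain is likely but not shown. A modest shift spread across many children might thus leave little trace in the safety tables.

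**Working it through.** **Tracing each effect from collection to analysis**

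| Effect | Graded measure, both arms | Named analysis | Other planned route |
|---|---|---|---|
| Irritability | ABC-Irritability: screening, Weeks 6, 12, 16, 24 | None in Protocol 8.8-8.9 or the SAP | AE form, modified for oxytocin-specific effects |
| Decreased appetite | Weight: screening, baseline, Weeks 12, 24 | None in Protocol 8.8-8.9 or the SAP | AE form, which asks about appetite directly |

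The SAP's named secondary outcomes are the SRS, Caregiver Strain and CGI-I response. The plan states no figure on this point, so there is none to reproduce.

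**Size, as an illustration only**

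From the documents: 35 per arm (Phase 2, n=70, 1:1; Protocol 3.1) and 25 per arm (Protocol 8.9). Assumed: two-sided 0.05; a rise of 0.5 SD with oxytocin; baseline-to-Week-12 correlation r of 0.5 or 0.7; an AE recorded in p0 = 10% or 20% of controls.

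Scale: two-sample t-test power (noncentral t, 2n-2 degrees of freedom) with standardised effect
- no baseline adjustment: 0.5
- change score: 0.5/√(2(1-r)), which is 0.5 at r=0.5 and 0.5/0.775 = 0.645 at r=0.7
- baseline-adjusted: 0.5/√(1-r²), which is 0.577 at r=0.5 and 0.700 at r=0.7

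AE count: a yes/no event when a threshold is crossed, so p1 = 1 - Φ(Φ⁻¹(1-p0) - δ). A treatment-emergent event is a change from baseline, so δ is taken on the change scale.
- δ = 0.5: 10% becomes 21.7%, and 20% becomes 36.6%
- δ = 0.645: 10% becomes 26.2%, and 20% becomes 42.2%

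Power, with exact enumeration for the two AE tests:

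| | n=25 per arm | n=35 per arm |
|---|---|---|
| Scale, unadjusted (also change score, r=0.5) | 41% | 54% |
| Scale, change score, r=0.7 | 61% | 76% |
| Scale, baseline-adjusted, r=0.5 / 0.7 | 52% / 68% | 66% / 82% |
| AE count, δ=0.5, Fisher | 11-16% | 17-25% |
| AE count, δ=0.5, chi-square | 21-27% | 27-34% |
| AE count, δ=0.645, Fisher | 21-28% | 32-43% |
| AE count, δ=0.645, chi-square | 34-41% | 43-53% |

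Setting the baseline-adjusted scale against only the δ=0.5 Fisher row would overstate the contrast, because it credits baseline information to the scale alone. On equal terms at n=35 and r=0.7, the change score has 76% (82% with baseline adjustment) against 32-53% for the AE count. The scale is the more sensitive in every matched comparison tried. The single yes/no event is itself a simplification, since the SAP names no test for AEs and plans totals and domains.

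**The case against.** The strongest reply is that a planned route already exists. The AE form is a semi-structured interview adapted to oxytocin, with drug-specific queries and a direct appetite question (Protocol 4.3). It is given in all groups at 6 of 12 sessions (5.2) and again at Weeks 12, 16 and 24 (Appendix A). Severity is graded and changes in severity are documented (8.5), and totals or counts and domains are compared by arm. This stands. A reader might infer that a rise in irritability would go unreported altogether, or that safety rests on a bare yes/no call; the documents support neither.

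The evidence for the effects is also thinner than it may look. Section 1.1 says the published studies were mostly single-dose challenges in adults, so only the adolescent study is clearly in youth, and its effects were mild to moderate. The protocol's general side-effect paragraph in section 1 opens with "Side effects of IN-OXT may include nasal irritation, runny nose, or tearing of the eyes, as well as an allergic reaction" and names neither irritability nor decreased appetite. A reader might call irritability the best-documented harm, or take the exclusion above 19 as a sign of concern about the drug. The first is not shown, and section 3.3 gives no reason for the second.

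Finally, the ABC is completed by caregivers who know the arm, and the arms differ in behavioural programme as well as drug. That limits what an ABC difference could mean, but it does not justify leaving the data out of the safety report.

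**Conclusion.** The gap holds in a limited form. ABC-Irritability and weight bear on two effects the protocol names and are collected in both arms, yet no analysis of either is planned. A moderate between-arm shift in either could go unreported if it is not recorded as an AE, and the unquantified severity rule in Protocol 8.2 makes that plausible for irritability already present at entry.

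For a 0.5 SD shift at 35 per arm, the scale would have about 54-82% power and a yes/no AE count about 17-53%. The shift, correlation and event rates are assumptions. The direction is stable over the ranges tried; the margin is not. No calculation was made for weight, where the point rests on the document trace alone. This is a minor improvement to the reporting of part (A) of the primary aim and does not show the safety plan to be unsound.

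**What to change.** Add two items to the SAP safety section:

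1. ABC-Irritability at Weeks 6 and 12 by arm, adjusted for the screening score, using the mixed-model form already in the SAP, with the between-arm difference and its 95% interval.
2. Weight at Weeks 12 and 24 by arm, adjusted for baseline, with a 95% interval. Children of this age are growing, so standardise for age if the team chooses a growth reference; the documents name none.

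Present both as supportive estimates beside the AE ratings, and state that caregivers know the arm and that a difference cannot be attributed to oxytocin alone. Do not use a count of children above 19 as a harm measure. That figure is an entry limit, and because entry is truncated there, some later scores above it are to be expected in both arms. If it is shown at all, label it descriptive.

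The cost is a short SAP addition and two tables from data already scheduled, with no new visits or measures.

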4.3. Safety Assessments

Adverse events will be systematically reviewed by study clinician and each study will have a back-up physician to assess safety. The study clinician will also do a general inquiry about health, other medications, and visits to medical care providers since the last visit. The following safety measures will be completed either in-person or may take place virtually via a HIPAA compliant platform (i.e. Zoom) if needed to reduce the amount of in person interaction between study team and participant.

- *Clinical Global Impressions – Improvement Scale – Global (CGI-I)*. The CGI-I employs a seven point (1 = very much improved to 7 = very much worse) to determine the patient's improvement in response to treatment. The CGI-I has been successfully used as an outcome measure in previous psychopharmacology trials including the RUPP trial of risperidone in children with ASD, and the STAART funded citalopram trial. The rating convention for assigning CGI scores is to use all available data including direct observation, scales, and patient report to inform clinical judgment. CGI-I, Global will be used to evaluate safety, with the requirement that individuals scoring CGI of 6 or greater for 2 or more weeks be discontinued from the study and provided with appropriate referrals.
- *Adverse event rating form*
This is a semi-structured interview that has been modified to assess OXT specific side effects for a recently completed pediatric trial of sustained oxytocin treatment in ASD ⁵². It contains a general inquiry, drug-specific queries, as well as several questions about daily activities (e.g., sleep, appetite, energy level, bowel and bladder function). This instrument has been widely used in other autism related clinical trials. In addition to these measures, vital signs (heart rate, blood pressure) will be measured biweekly at the following visits: screening, baseline/week 1, week 3, week 5, week 7, week 9, week 11, week 12, week 16, and week 24 (or another biweekly schedule depending on start days/dates) Standardized procedures will be used for all physical measurements. We will attempt to do vital signs following a 4 minute period of rest, with the participant seated. Height and Weight will be taken at screening, baseline, Week 12, and Week 24 with all outer wear and shoes removed at every visit.

5. Study Treatment

